Endpoints for Evaluation:

Primary: To compare the relationship of once daily tacrolimus extended release (Envarsus) versus twice daily tacrolimus immediate release (Prograf) doses to achieve target trough concentrations (C) relative to the total daily dose (D) given

and the effect of C/D ratio on renal function at day 7 and months 1, 3, 6, and 12 months after transplantation utilizing concentration to dose ratio (C/D ratio).

Secondary: Comparison between treatment cohorts regarding incidence will rely upon assessments for each of the following results:

- Compare incidence of rejection between the groups at 90 and 365 days post-transplant (Banff grade I-III and antibody mediated rejection [AMR])
- Compare graft loss and death within 1 year post-transplant
- Compare and summarize serious adverse events (AEs) between study groups
- Death within 1 year post-transplant

Statistical Analysis:

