Sample Size: The sample size for this pilot study is not sufficiently powered to document that the C/D ratio in each patient group will correlate directly with eGFR. We expect to see a trend suggestive that the Envarsus group by virtue of more stable Tacrolimus level and greater compliance over time will be less likely to develop calcineurin-induced nephrotoxicity and therefore result in a better e-GFR. This is not likely to be statistically significant in this inadequately powered study since the variability in donor organs themselves, as well as many other variables, will not permit a precise analysis in this small study sample. However, stratification for living donors and deceased donors may provide important trends in this pilot project which may then guide us to expand the study in more restricted categories of renal allograft recipients. The statistical summary and analysis of safety data, will consist of all subjects who enrolled into the study and took at least one dose of study medication. Demographics and other baseline characteristics will be summarized by treatment group. Descriptive statistics (e.g., n, mean, standard deviation, minimum, median, maximum) and interquartile range, coefficient of variation, and geometric mean will be provided for tacrolimus dose and whole blood concentrations of tacrolimus for both study cohorts. Tacrolimus concentrations will be summarized with descriptive statistics. The analysis of efficacy regarding C/D effectiveness in relation to number of rejection episodes and outcomes at various stated time points will be conducted using Student T test. The association between whole blood concentrations and the following endpoints will be assessed: rejection episode and eGFR, histopathology (Banff classification) and conventional measures of transplant outcomes.

H0: The probability of incidence for the primary endpoint is the same between patients receiving Envarsus and patients receiving immediate-release tacrolimus.

Safety: All adverse events (AE) will be listed. The number and percentage of AEs, significant AEs, AEs leading to discontinuation, and AEs related to study drug will be summarized by treatment group. The number and percentage of AEs by severity will also be summarized.

Randomization will be performed in excel prior to initiation: Allocation will consist of a 1:1 ratio for twice daily, immediate-release tacrolimus or Envarsus.

Institutional Review Board (IRB)

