Version Date: 11Jun2019 8 of 16 populations (race, sex, age, and diabetes) should provide evidence for possible greater efficiency and lesser toxicity of extended release drug, Envarsus, as compared to SOC treatment with immediate release tacrolimus given twice per day. Envarsus is an oral, extended-release formulation of tacrolimus developed to enable a once daily dosing regimen. It decreases intra-patient variability and offers flatter kinetics which should ensure a more consistent immunosuppression exposure over the long-term without unpredictable high peaks which may be related to higher toxicity rate, including nephrotoxicity. There is little doubt that the once daily dosing has been described as improving medication adherence [Sabbatini et al, 2014; Doesch et al, 2013; Eberlin et al, 2013; Kuypers et al, 2013].

Since Tacrolimus, the mainstay of immunosuppression in renal transplant patients is known for drug induced nephrotoxicity, which may limit graft survival we propose a prospective randomized study to analyze the relationship of tacrolimus doses to achieve target trough levels (C/D) and renal function at different time-points after transplantation. In this analysis, all 1:1 randomized renal allograft recipients maintained with mycophenolate sodium will be treated either with tacrolimus (Prograf) in the SOC treated controls or with Envarsus in the experimental group. Renal function will be estimated by MDRD equation (eGFR MDRD). Such a prospective, randomized, controlled pilot trial to compare the use of once a day Tacrolimus (Envarsus) vs. twice a day Tacrolimus (Prograf) to test the hypothesis that the consistency of immunosuppression with Envarsus increases the C/D ratio, i.e. get effective stable trough levels with lower total Tacrolimus dose given as Envarsus, and lead to better eGFR, and reduce the likelihood of nephrotoxicity (lower total Tacrolimus exposure). In the course of this study, patients in the control arm will receive immediate-release formulations of tacrolimus in accordance with local SOC dispensing practices, thus preserving the real-world conditions in which the patient could receive any manufacturer's approved product. In this manner, it is hoped that this research will improve the understanding of chronic calcineurin inhibitor injury and provide greater insight into how tacrolimus exposure impacts long term, and even short term, renal function (eGFR).

Pharmacokinetics

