At these visits, the following study procedures and tests will occur:

- A review of any medications you take
- Adverse Events review
- Arm 1 (Envarsus) only: Return any used and unused bottles of study drug (week 52 only)

Study Drug Handling

Current ICH GCP Guidelines require the investigator to ensure that study drug deliveries from the Sponsor are received by the investigator/or designee and ● that such deliveries are recorded, ● that study drug is handled and stored

according to labeled storage conditions, • that study drug with appropriate expiry is only dispensed to study subjects in accordance with the protocol. Drug inventory and accountability records for the study drugs will be kept by the investigator / research pharmacy.

Study drug accountability throughout the study must be documented and reconciled. The following guidelines are therefore pertinent: • The investigator agrees not to supply study drugs to any persons except the eligible subjects in this study in accordance with the protocol. • The investigator or designee will keep the study drugs in a pharmacy, accessible only to those authorized by the investigator to dispense these test drugs. • A study drug inventory will be maintained by the investigator or designee. The inventory will include details of material received and a clear record of when they were dispensed and to which subject. Appropriate forms of deliveries and returns must be signed by the site staff delegated this responsibility. • The site will return study drug to the Sponsor at the end of the study or upon expiration.

Medication will be dispensed by the research pharmacy. Tacrolimus, immediate-release will be obtained by the transplanting center during a participant's inpatient stay and by the patients, themselves, thereafter, at retail pharmacies.

Data collection

Demographics: Will be collected during screening: date of birth, sex, race, and ethnicity.

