Medical History: Etiology of renal failure, viral serology (HBV, HCV, CMV, EBV), and diabetes history (as applicable). *Transplant Information*: Day 0 visit: type of transplant (living related, living non-related, DD, and whether organ was obtained in the setting of DCD or CDC), number of prior transplants and reason for prior graft loss (if applicable), total cold and warm ischemia time in hours and minutes, KDPI, ABO blood typing, HLA typing of donor and recipient, degree of HLA mismatch between donor and recipient, and most recent panel reactive antibody testing. Donor viral serology information (HBV, HCV, CMV, EBV), if available, will be collected and recorded. Additional donor information includes age, sex, height, weight, donor cause of death, ethnicity, ABO typing, and results of any pre-implantation biopsies. *Height and Body Weight*: Height and dry weight will be recorded at screening and pre-operatively on study day 0.

Efficacy Assessment

Estimated Glomerular Filtration Rate: Estimated glomerular filtration rate (eGFR) will be calculated at day 7 and months 1, 3, 6, and 12 using the Modification of Diet in Renal Disease (4 variable – MDRD) criteria.

Calculation of C/D Ratio: Calculation of the daily trough level over the average daily total tacrolimus dose delivered either by ENVARSUS or by SOC twice a day Tacrolimus will be performed monthly throughout the study.

Patient Survival: Patient survival is any subject that is known to be alive at the study conclusion.

Graft Survival: Graft survival is defined as any subject that does not fit the following definition of graft loss: subject death, re-transplantation, transplant nephrectomy, or return to dialysis for a period of ≥6 weeks by study end. *Acute Rejection*: For study purposes, diagnoses of rejection require biopsy confirmation. Both acute cellular and antibody mediated rejection will be assessed and graded according to published criteria [Solez et al, 2008] by the NYPH

Renal Pathology Division pathologist.

Adverse Events

Adverse event collection will begin once informed consent has been signed and continue throughout the subject's participation in the study. A subset of the routine laboratory assessments obtained per SOC, including creatinine, hemoglobin, hematocrit; platelet count; white blood cell count; serum sodium, potassium, blood urea nitrogen, glucose, urinalysis (including urinary protein), tacrolimus trough concentrations.

Physical Examination

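### The C/D–eGFR part of the primary endpoint has no stated model and no adjustment for age, sex or race, so a relation that is not randomized is open to demographic confounding, partly through the MDRD equation

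*Combined protocol and SAP*

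**What the plan says.** - **Endpoint.** Endpoints for Evaluation makes the second part of the primary endpoint "and the effect of C/D ratio on renal function at day 7 and months 1, 3, 6, and 12 months after transplantation".
- **Outcome measure.** The Background states: "Renal function will be estimated by MDRD equation (eGFR MDRD". Efficacy Assessment fixes the version and repeats the five time points: eGFR is calculated "using the Modification of Diet in Renal Disease (4 variable – MDRD) criteria". The coefficients are not printed.
- **Analysis.** Statistical Analysis says that efficacy regarding C/D, in relation to rejection episodes and outcomes, "will be conducted using Student T test". It adds: "The association between whole blood concentrations and the following endpoints will be assessed: rejection episode and eGFR". That second sentence concerns concentration, not C/D, and gives no method. There is no regression, slope or covariate list.
- **Other variables.** Living versus deceased donor is the only stratification mentioned, and donor-organ variability is the first reason given for imprecision. Demographics are to be summarized by arm.
- **Data available.** Data collection lists "date of birth, sex, race, and ethnicity" at screening. The Background speaks of "populations (race, sex, age, and diabetes) should provide evidence for possible greater efficiency and lesser toxicity" of the extended-release product, but this does not carry through to the analysis.

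**The concern.** Patients are randomized to a formulation, not to a C/D ratio. C/D is observed after randomization, and the Background treats it as a marker of how fast the patient metabolizes tacrolimus. Comparing eGFR between patients with high and low C/D is therefore an observational analysis, even inside a randomized trial.

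Age, sex and race could distort it in two ways. They may go with real differences in kidney function, which would confound the relation under any measure of GFR. They are also multipliers inside the 4-variable MDRD value. If a multiplier is inexact in transplant recipients and C/D differs across that characteristic, two groups with the same true function get different eGFRs, and the difference lines up with C/D.

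At stake is the trend that the pilot is meant to pass on to a larger study. A trend is read from a point estimate, so bias matters even where no claim of significance is made.

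**Working it through.** The plan states no figure for this relation, so there is none to reproduce.

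**Inputs from the documents:** 50 patients, 25 per arm; 4-variable MDRD; eGFR at day 7 and months 1, 3, 6 and 12.

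**Assumed, not in the documents:** the standard MDRD form (creatinine exponent −1.154, age exponent −0.203, factors 0.742 for female sex and 1.212 for race); eGFR about 55; residual SD of log eGFR 0.3; within-group SD of log C/D 0.45; 20% to 40% of recipients in the race category (p); their geometric mean C/D 0.6 to 0.9 of the others' (r). Let f be the part of the race factor that does not reflect true function: f = 1 if the factor is right, f = 1.212 if it is wholly spurious.

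**Step 1. Bias through the race factor alone.** The induced slope per log unit of C/D is

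b = p(1−p)·ln r·ln f / [0.45² + p(1−p)·(ln r)²].

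The change per doubling is 55 × (2^b − 1).

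| f | p | r | b | mL/min per doubling |
|---|---|---|---|---|
| 1 | any | any | 0 | 0 |
| 1.10 | 0.2 | 0.9 | −0.008 | −0.3 |
| 1.212 | 0.3 | 0.75 | −0.053 | −2.0 |
| 1.212 | 0.4 | 0.6 | −0.089 | −3.3 |

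Central row: 0.21 × (−0.288) × 0.192 / (0.2025 + 0.0174) = −0.053. The sign reverses if C/D is higher in that group.

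**Step 2. Against noise.** In the central row the SD of log C/D is √0.2199 = 0.469, so the standard error of the slope is about 0.3 / (0.469 × √49) = 0.091. The bias is 0.053 / 0.091 = 0.6 standard errors. In the last row the SD is √0.2651 = 0.515, the standard error 0.083 and the ratio 1.1. With f = 1.212, simulated rejection rates of a nominal 5% test with no true relation are about 5% (p = 0.2, r = 0.9), 8% to 9% (central row) and 17% (last row).

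**Step 3. All three characteristics together.** A separate simulation used n = 50, 1,500 runs per scenario, no true relation, SD of log C/D 0.40, and various links of C/D with race, sex and age.
- Factors exactly right: the unadjusted slope is about 0 and false positives about 5%, even when C/D is linked to the demographics.
- Half of each factor spurious: slope −4.5 to +2.2 mL/min per log unit, false positives 5% to 12%.
- Factors wholly spurious: slope −8.8 to +4.9, false positives 4% to 28%. Opposing race and sex links can cancel to about 0.

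The −8.8 extreme is 8.8 × ln 2 = 6.1 mL/min per doubling. Its mean correlation of −0.19 is 0.193 × √48 / √(1 − 0.193²) = 1.4 standard errors. It needs every factor wholly wrong and all three links pulling the same way.

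**Step 4. Arm comparison.** In every scenario the simulated between-arm difference in eGFR is centred on 0 (−0.3 to +0.3 mL/min).

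**Step 5. With adjustment.** On the log scale,

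ln eGFR = constant − 1.154 ln(creatinine) − 0.203 ln(age) + ln(0.742)·female + ln(1.212)·race.

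Once log age, sex and race are covariates, they absorb the last three terms whatever their coefficients. The log C/D coefficient is then exactly −1.154 times the one from log creatinine with the same covariates. In a simulated data set of 50, three different sets of demographic factors gave an adjusted coefficient of 0.0283 each time, while the crude slope moved from −0.005 to 0.048. In the Step 3 scenarios, adding age, sex and race brought the mean slope to between −0.5 and +0.4 and false positives to 4% to 6%.

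**The case against.** A reader might infer that any link of C/D with age, sex or race enters the slope as if it were kidney function. The documents do not support that. The demographic terms are there to offset differences in creatinine generation; where they are right, the artefact is zero (Steps 1 and 3). A real difference in GFR between groups is ordinary confounding and not a fault of MDRD.

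Four further points stand:
- The plan specifies no slope, so the more basic gap is the missing model; missing covariates are one part of it. In a within-patient analysis the sex and race factors would cancel and age would hardly change.
- The documents give no C/D by demographic group, no racial mix and no SDs. The Background sentence names populations in which to compare the products; it does not say that C/D varies between them.
- On central inputs the bias is 0.6 standard errors, in a pilot that already describes itself as underpowered for this correlation.
- Demographics alone would be an incomplete adjustment, since the plan itself puts donor organs first among the sources of variability.

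These points limit the size of the concern but do not remove it. The endpoint still asks for an effect of C/D on renal function, the analysis text gives no way to estimate it, and nothing in the documents shows that the factors are exact in these recipients.

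**Conclusion.** The concern holds in a limited form. The C/D–eGFR relation is part of the primary endpoint, is observational, and has neither a model nor demographic adjustment, although the data are collected.

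Neither the size nor the sign of the bias can be derived from the documents. Under the assumptions above, the race factor alone gives from zero to about 3 mL/min per doubling of C/D, at most about one standard error at n = 50. The joint extreme of about 6 mL/min requires all three factors to be wholly spurious and aligned. These figures cover only the route through the equation; confounding through real differences in kidney function is not quantified.

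A reader might also infer that the randomized comparison of eGFR between arms is compromised. It is not, in expectation.

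**What to change.** In Statistical Analysis, state that log eGFR is regressed on log C/D with arm, donor type (living or deceased), log age, sex and race as covariates, either at each of the five stated time points or in one repeated-measures model, and say which. Report the slope per doubling of C/D with its 95% CI, labelled exploratory. For the C/D coefficient to be free of the MDRD demographic factors, use the same age as in the eGFR calculation and a race coding that separates the category the equation uses.

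The cost is wording only, since all variables are already collected. An unadjusted slope in 50 patients leaves 50 − 2 = 48 degrees of freedom. The five added covariates take five if race is binary, leaving 43, and more with further race categories.

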Study participants will receive either Envarsus (single daily dose) or SOC, twice daily, immediate-release tacrolimus for 1 year following their transplant procedure. Because of its extended-release pharmacokinetics, it is critical that Envarsus be initiated at a dose of 0.12/mg/kg/day as a single daily dose. After the initial dose, Envarsus dosing will be titrated according to the clinical judgment of the attending physician and appropriate TDM of tacrolimus trough concentrations. This dosing should account for the fact that when identical trough levels are targeted, systemic exposure to tacrolimus is the same for both Prograf and Envarsus. Patients receiving immediate-release tacrolimus should be initiated on therapy per center protocol which is 0.1 mg/kg/day. After initial dosing, subsequent dosing in patients receiving either Envarsus or immediate-release tacrolimus should be predicated on clinical experience, patient tolerability, and monitoring of whole blood tacrolimus drug concentrations, the measurement of which, along with target tacrolimus levels, will be guided by the center protocol.

Study subjects will be counseled on the need to exhibit 100% compliance with their medication regimen in a manner that reflects a center's own standard of care.

Investigational Product and Dosing:

Tacrolimus, extended-release, oral (Envarsus); 0.75 mg, 1 mg, 4 mg tablets

Administered once daily at initial weight-based dose of 0.12 mg/kg. Dosing and monitoring thereafter predicated on clinical judgment to a minimum whole blood tacrolimus concentration of at least 8 ng/mL. When possible, patients will receive their daily dose of Envarsus using the fewest number of pills possible.

Comparative Drug and Dosing:

Tacrolimus immediate-release, oral; 0.5 mg, 1 mg, 5 mg capsules

Administered twice daily per clinical judgment of supervising physician (dosing and monitoring in accordance with center protocol) to a minimum whole blood tacrolimus concentration of at least 8 ng/mL.

Concomitant Medications:

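### No planned analysis of C/D uses body weight, although it is recorded: this may cost precision in the randomised arm comparison and leaves the C/D–eGFR association open to confounding by recipient size

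*Combined protocol and SAP*

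**What the plan says.** The primary endpoint (Endpoints for Evaluation) has two halves. One compares the arms on "doses to achieve target trough concentrations (C) relative to the total daily dose (D) given". The other is "and the effect of C/D ratio on renal function at day 7 and months 1, 3, 6, and 12 months after transplantation". Under Efficacy Assessment, the ratio is the "Calculation of the daily trough level over the average daily total tacrolimus dose delivered" in either arm. No unit is printed. Milligrams is the natural reading, because the tablets and capsules are listed in mg.

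Both arms start by weight. For Envarsus the plan has "Administered once daily at initial weight-based dose of 0.12 mg/kg", and immediate-release patients "should be initiated on therapy per center protocol which is 0.1 mg/kg/day". After that, "subsequent dosing in patients receiving either Envarsus or immediate-release tacrolimus should be predicated on clinical experience, patient tolerability, and monitoring of whole blood tacrolimus" levels, so later doses are not set per kilogram.

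Weight is available: "Height and dry weight will be recorded at screening and pre-operatively on study day 0". The Schedule of Events table also marks height and weight at Months 1–12, but its footnote gives only screening and day 0.

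The Statistical Analysis section plans a Student t test, associations of unspecified form between tacrolimus concentrations and outcomes including eGFR, a possible split by donor type, and a baseline summary by arm. It names no covariate. Weight could enter only through the baseline summary.

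**The concern.** A ratio to total dose may partly reflect how large the patient is. Whether it does depends on whether trough per mg falls with weight. If so, the two halves of the primary endpoint are affected differently.

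- **Arm comparison.** Allocation is randomised 1:1, so the expected bias from weight is zero. Weight still adds variance, and with 25 per arm the arms can differ in weight by chance.
- **C/D–eGFR association.** Nobody is randomised to a C/D value. If heavier recipients have lower C/D and also lower eGFR, size alone makes higher C/D go with better eGFR. That is the direction the Background section hypothesises. The plan expects only a trend and would use trends to guide a larger study, so a small spurious correlation could mislead it.

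**Working it through.** The plan states no effect size, standard deviation or power for C/D, so there is no figure of its own to reproduce.

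**Inputs from the documents:** 25 patients per arm, 50 in all; D is total daily dose; no covariate.

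**Assumptions, not in the documents:** C/D proportional to weight^(−b), with b = 0, 0.5 or 1; weight CV 20–25%; log-SD of C/D from all other sources t = 0.35–0.55; eGFR proportional to weight^(−c), with c = 0.25–0.75; other log-SD of eGFR 0.35.

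**Step 1, log-SD of weight.** s = √ln(1 + CV²) = 0.198 at CV 20% and 0.246 at CV 25%.

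**Step 2, share of log C/D variance due to weight.** R² = (bs)² / ((bs)² + t²).
- b = 1: lowest 0.0392/(0.0392 + 0.3025) = 11.5%; highest 0.0606/(0.0606 + 0.1225) = 33%.
- b = 0.5: lowest 0.0098/(0.0098 + 0.3025) = 3%; highest 0.0152/(0.0152 + 0.1225) = 11%.
- b = 0: 0%.

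Adjustment is worth 1/(1 − R²) − 1 more patients.

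**Step 3, chance imbalance (95% limit).** Shift in the C/D ratio = exp(1.96·b·s·√(2/25)) − 1.
- b = 1: 11.6% (s = 0.198) to 14.6% (s = 0.246).
- b = 0.5: 5.6% to 7.1%.

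**Step 4, correlation induced between log C/D and log eGFR.** r = b·c·s² / (√(b²s² + t²)·√(c²s² + 0.35²)), at a middle value s = 0.22.
- b = 1: 0.06 (t = 0.55, c = 0.25) to 0.23 (t = 0.35, c = 0.75).
- b = 0.5: 0.03 to 0.13.
- b = 0 or c = 0: zero.

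Letting s run over 0.198–0.246 widens these to 0.05–0.27 and 0.02–0.15.

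| b | Weight share of log C/D variance | Adjustment worth (more patients) | Chance shift in C/D ratio | Induced correlation |
|---|---|---|---|---|
| 0 | 0% | 0% | 0% | 0 |
| 0.5 | 3–11% | 3–12% | 6–7% | 0.03–0.13 |
| 1 | 11.5–33% | 13–49% | 12–15% | 0.06–0.23 |

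**Step 5, effect on a nominal 5% test with all 50 patients.** By Fisher's z, f = atanh(r)·√47 and P = 1 − Φ(1.96 − f) + Φ(−1.96 − f). With no true C/D–eGFR link, an induced r of 0.03, 0.06, 0.12 or 0.20 gives a nominally significant result 5.5%, 7.0%, 13.1% or 28.5% of the time.

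**Step 6, dividing by mg/kg instead.** The log variance becomes (1 − b)²s² + t² in place of b²s² + t². The ratio of new to old is 1.13–1.50 at b = 0, 1.00 at b = 0.5 and 0.67–0.89 at b = 1. Normalising the ratio adds noise whenever b is below 0.5.

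**The case against.** **The per-kilogram start does not make C/D track size.** At a trough of 8 ng/mL on the Envarsus starting dose, C/D is 8/7.2 = 1.11 at 60 kg and 8/12 = 0.67 at 100 kg. A reader might infer a 40% effect of weight. The documents do not support that. If trough is proportional to dose, C/D is the same whatever dose is given. The example assumes that both patients reach the same trough on the same mg/kg dose, which is the point at issue, and the two weights are illustrative. Later doses follow levels, and C/D is calculated monthly, mostly after titration. This objection stands: the effect depends on b, and b may be near zero.

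**The arm comparison is randomised.** A reader might infer that both halves of the endpoint are confounded. Only the C/D–eGFR half is.

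**The gain in the arm comparison is modest.** Take a total C/D CV of 50% (log-SD 0.472), weight CV 20% and a true ratio of 1.3. Power ≈ Φ(ln 1.3/(SD·√(2/25)) − 1.96) is 50% unadjusted. After adjustment it is 50%, 52% or 58% for b = 0, 0.5 or 1. The plan already calls itself an underpowered pilot and concedes that other sources of variability preclude precision. That limits the seriousness, but low power does not excuse a confounded association, and weight is not named.

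**Weight is one candidate among several.** The documents also mention donor type, race, sex, age, diabetes and CYP3A metabolism, and the C/D–eGFR model itself is unspecified. This is fair: a weight term is part of that larger gap. It is still a cheap part to close, because the value is already recorded.

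**The C/D definition is deliberate.** It follows a cited report that uses concentration normalised by dose. Nothing here makes that definition an error.

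**Conclusion.** The point holds as a missing adjustment on the primary endpoint. The omission is certain from the text; its size is not, since b, the spread of weight and any weight–eGFR link are all assumed.

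For the arm comparison, the consequence is lost precision and exposure to chance imbalance, from nothing at b = 0 to the upper values in the table at b = 1. For the C/D–eGFR association, the consequence is possible confounding, which needs both b > 0 and an eGFR that falls with weight. This second consequence is the stronger reason to act. The declared exploratory, underpowered design keeps the matter to a worthwhile improvement and does not make it a flaw that invalidates the trial.

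**What to change.** In the Statistical Analysis section:

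1. Compare log C/D between arms with a linear model containing arm and log day-0 dry weight.
2. Include log weight in whatever model is specified for C/D and eGFR.
3. Report the unadjusted results beside both.
4. State the unit of C/D. Keep its definition, and do not use a mg/kg version in the primary analysis; it can serve as a sensitivity analysis.

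Reconcile the Schedule of Events with its footnote on whether weight is measured at Months 1–12. This decides whether a time-matched weight exists, but the day-0 value suffices for the change above.

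The cost is SAP wording and one degree of freedom per model. No new measurement is needed. The model estimates the weight slope from the data, so if b is near zero little is lost and nothing is gained.
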